11.3 Significance Testing and Estimations

A 90% confidence interval (CI) will be calculated for the geometric least square mean ratios from analysis of variance (ANOVA) on the log transformed C_{max} , AUC_{inf} and $AUC_{0-tlast}$ to illustrate the difference between renal impaired group versus the control group with normal renal function.

Moreover, 90% CI of the median difference for t_{max} will be produced.

The statistical analysis of safety is only descriptive therefore no formal statistical significance testing will be performed.

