An analysis of variance (ANOVA) will be performed separately for the groups with a renal impaired function, on the natural log-transformed telotristat ethyl and the active metabolite (telotristat) C_{max} , $AUC_{0-tlast}$, and AUC_{inf} . The repeated-measures ANOVA, which takes into account the fact that the measures are correlated, will be performed using a linear mixed effects model, with renal function group as a fixed term. An estimate and 90% CI for the geometric least squares mean (LSM) ratios for each renal impaired group (test) versus the control group with normal renal function (reference) will be provided for C_{max} , $AUC_{0-tlast}$, and AUC_{inf} .

Ratios of LSM will be calculated using the exponentiation of the difference between treatment LSM from the analyses on the log-transformed C_{max} , $AUC_{0-tlast}$, and AUC_{inf} . These ratios will be expressed as a percentage relative to the reference group (test [mild, moderate, or severe renal impaired groups] versus reference [control group with normal renal function]). The 90% CIs will be obtained for the difference between the LSM (test minus reference) resulting from the analyses of the log-transformed C_{max} , $AUC_{0-tlast}$, and AUC_{inf} .

The t_{max} will be analysed using nonparametric analysis (Walsh averages and appropriate quantile of the Wilcoxon signed rank test statistic). The median difference between the test and reference groups and the corresponding 90% CI for the difference will be calculated.

Protein binding

The following parameter will be determined (where possible) for telotristat ethyl, its active metabolite (telotristat) and the inactive metabolite LP-951757: f_u unbound plasma fraction.

PK parameters may also be expressed in terms of unbound concentrations (e.g. C_{maxu} , AUC_u , CL_u/F), if applicable.

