- $MRAUC_{0-infuTotalNorm} = (AUC_{0-infu} \text{ LP-778902/MW}_{LP-778902}) / (AUC_{0-infu} \text{ LP-778902/MW}_{LP-778902} + AUC_{0-infu} \text{ telotristat ethyl/MW}_{telotristat ethyl})$
- $MRAUC_{0-tlastuTotal} = (AUC_{0-tlastu} \text{ LP-778902}) / (AUC_{0-tlastu} \text{ LP-778902} + AUC_{0-tlastu} \text{ telotristat ethyl})$
- $MRAUC_{0-tlastuTotalNorm} = (AUC_{0-tlastu} \text{ LP-778902/MW}_{LP-778902}) / (AUC_{0-tlastu} \text{ LP-778902/MW}_{LP-778902} + AUC_{0-tlastu} \text{ telotristat ethyl/MW}_{telotristat ethyl})$

3.1.5 *Safety endpoints*

The safety endpoints are:

- AEs;
- Clinical safety endpoints: physical examination, vital signs, 12-lead ECGs;
- Clinical laboratory tests: haematology, coagulation, biochemistry, urinalysis;
- Pregnancy tests at screening, Day -1 and EOS/ Early discontinuation visit.

3.1.6 *Multiplicity*

A multiplicity correction will be used in the statistical analysis to compare renal impaired function groups to the healthy group. A Bonferroni procedure will be used to keep the overall type 1 error equals to 10%. For each test, the statistical level of significance will be 10% divided by the number of hypotheses tested.

3.1.7 *Significance testing and estimation*

A 90% confidence interval (CI) will be calculated for the geometric least square mean ratios from the analysis of the variance (ANOVA) on the log transformed C_{max} , AUC_{0-inf} and $AUC_{0-tlast}$ to illustrate the difference between renal impaired group versus the control group with normal renal function. If the data permitted, 90% CI will also be calculated for PK parameters of the unbound fractions.

Moreover, 90% CI of the median difference for t_{max} will be produced using Hodges-Lehmann estimation.

The statistical analysis of safety is only descriptive therefore no formal statistical significance testing will be performed.

3.2 **Analysis methods**

3.2.1 *Efficacy*

Not applicable.

3.2.2 *Pharmacokinetics*

The PK analysis will be performed by a non-compartmental approach using Phoenix[®] WinNonLin[®] version 7.0 (Pharsight) and will be performed on the PK population.

3.2.2.1 *PK parameters calculation*

The Ipsen PDM (Pharmacokinetics Drug Metabolism) instructions (version dated 20JUN2014) for PK parameters calculation will be followed.

The following rules will be used:

- Actual sampling times will be used for deriving PK parameters.

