Additionally, for each of the 3 analytes, a linear-linear plot will be performed for C_{max} , AUC_{0-inf} and $AUC_{0-tlast}$, with individual PK parameters (y-axis) versus the respective individual estimated GFR value at baseline (x-axis). All subjects will be on the same graph.

An ANOVA will be performed separately for each renal impaired function group on the natural log-transformed C_{max} , $AUC_{0-tlast}$ and AUC_{0-inf} for both telotristat ethyl and its active metabolite with renal function group as a fixed term. Geometric mean ratios and corresponding 90% CI for each renal impaired group (Test) versus the healthy control group (Reference) will be computed using the following sample SAS code:

```
proc mixed data=ADPP;
  where=<Renal function group> in (Healthy Severe
    /* (Healthy Moderate) (Healthy Mild) */);
  model log(AVAL) = <Renal function group>;
  lsmeans <Renal function group> / cl alpha=0.10/<nb of hypotheses>;
  estimate "Renal impaired / Healthy" <Renal function group> -1 1 / cl
  alpha=0.10/<nb of hypotheses>;
run;
```

The resulting least-squares (LS) means, difference in LS means between two groups (test minus reference), and corresponding 90% CIs will be exponentiated. The exponentiation of the difference in LS means will yield the estimated ratio of the PK parameter for a renal impaired function group relative to healthy subjects. These ratios will be expressed as a percentage relative to the reference group (test [mild, moderate, or severe renal impaired groups] versus reference [healthy group]).

For each test, a Bonferroni correction will be applied to adjust the statistical level of significance in order to keep the overall type 1 error equals to 0.10 (see section 3.1.6 for details).

No analysis will be performed if more than 1/3 of the values are not determined.

In case of exclusion of subjects in the severe renal impaired function group or in the healthy group, a sensitivity ANOVA will be performed with the included subjects and only including their matching subjects.

For t_{max} , an estimate of the median difference and 90% CI of the median difference will be provided using Hodges-Lehmann estimation, based on Walsh averages, using the following SAS code:

```
proc npar1way hl alpha=0.1 data= ADPP;
  where <Renal function group> in (Severe Healthy) and
    PARAMCD='TMAX';
  class <Renal function group>;
  var AVAL;
  exact hl;
run;
```

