3.2.2.4.3 Protein binding

Listings with unbound plasma concentrations (including unbound plasma fraction and PK blood sampling dates and times), unbound plasma PK parameters and metabolic ratios will be provided by renal function group and subject.

Descriptive statistics on plasma unbound concentrations of telotristat ethyl, its active metabolite telotristat (LP-778902) and its inactive metabolite (LP-951757) will be computed for each renal function group, overall and by gender.

Descriptive statistics on unbound PK parameters (including unbound fractions) and metabolic ratios for telotristat ethyl, its active metabolite telotristat (LP-778902) and its inactive metabolite (LP-951757) will be computed for each renal function group, overall and by gender.

Scatter plots and box-whisker plots will be presented for the comparison of C_{maxu} , $AUC_{0-tlastu}$, AUC_{0-inf} and unbound fractions of renal function groups versus healthy control group, overall and by gender.

If the data permitted, same ANOVA as above will be performed separately for each renal impaired function group on the natural log-transformed C_{maxu} , $AUC_{0-tlastu}$, AUC_{0-inf} and unbound fractions (fu; no log-transformed) for both telotristat ethyl and its active metabolite with renal function group as a fixed term. The same SAS code as the previous analysis will be used. Sensitivity analysis will also be conducted, the same method as described above will be used.

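### The SAP adds a Bonferroni correction that the protocol lacks, so if Part B runs the ANOVA intervals labelled 90% are 96.7% intervals, and SAP Section 5 does not declare the change

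*SAP*

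**What the plan says.** **Protocol.** Section 11.3 states: "A 90% confidence interval (CI) will be calculated for the geometric least square mean ratios". Section 11.4.4 makes this specific to each comparison: "An estimate and 90% CI for the geometric least squares mean (LSM) ratios for each renal impaired group (test) versus the control group". The synopsis agrees. None of these places mentions a multiplicity correction.

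**SAP, multiplicity.** Section 3.1.6 introduces a correction for comparing the impaired groups with the healthy group: "A Bonferroni procedure will be used to keep the overall type 1 error equals to 10" per cent, with each test at 10% divided by the number of hypotheses. Section 3.2.2.4.1 repeats it: "For each test, a Bonferroni correction will be applied to adjust the statistical level of significance".

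**SAP, code.** The sample code in 3.2.2.4.1 carries the division into the interval limits: "lsmeans <Renal function group> / cl alpha=0.10/<nb of hypotheses>". The ESTIMATE statement, which gives the ratio, has the same alpha.

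**SAP, label.** Section 3.1.7 keeps the protocol's 90% interval. The text after the code reads: "The resulting least-squares (LS) means, difference in LS means between two groups (test minus reference), and corresponding 90% CIs will be exponentiated". For the unbound parameters and unbound fractions, section 3.2.2.4.3 says: "The same SAS code as the previous analysis will be used".

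**SAP, declared changes.** Section 5 lists two changes from the protocol, the included population and the LP-951757 assay method, and states that there is no other.

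**The concern.** The SAP gives two incompatible specifications for the same interval: 90% by its label, 100(1 − 0.10/k)% by its code. They agree only when k = 1. Part B is a planned stage, and it runs only when Part A has shown a substantial effect. The mislabelling would therefore appear just when the intervals bear most on the study's purpose, which is to inform dose recommendations in renal impairment.

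Four further points follow.

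- The severe-versus-healthy interval, computed on the same 16 subjects, would depend on whether Part B was later run.
- The correction also widens the single-group LS-mean intervals, which test no hypothesis.
- The t_max code in the same section keeps alpha at 0.1 undivided, so the SAP is not consistent across parameters.
- SAP 1.3.4 repeats the 84% power without saying which alpha it assumes.

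**Working it through.** **Inputs.** CV 53%, eight subjects per group, a 2-fold difference and 84% power come from protocol 11.2 and SAP 1.3.4. Alpha 0.10/k comes from SAP 3.1.6 and the code. The SAP fits a separate two-group model for each impaired group, so df = 8 + 8 − 2 = 14. k = 1 if only Part A runs and k = 3 if Part B runs. That is a reading of SAP 3.1.6, which gives no number.

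**1. Reproduce the stated power.**
- Log-scale SD = sqrt(ln(1 + 0.53²)) = 0.4976
- SE of the log ratio = 0.4976 × sqrt(2/8) = 0.2488
- Noncentrality = ln 2 / 0.2488 = 2.786
- Noncentral t, 14 df, two-sided alpha 0.10: critical value 1.761, power **84.2%**. This matches the stated 84%.
- Two-sided 0.05 gives 73.6%, which does not match.

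**2. Interval width at k = 3.**
- Per-comparison alpha = 0.10/3 = 0.0333, so confidence = 96.7%
- Critical value 2.360 instead of 1.761; 2.360/1.761 = 1.340, so **34% wider** on the log scale

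| | k = 1 (90%) | k = 3 (96.7%) |
|---|---|---|
| Ratio interval, factor each side, exp(t × 0.2488) | 1.55 | 1.80 |
| Interval at an observed ratio of 2.0 | 1.29 to 3.10 | 1.11 to 3.60 |
| Single-group LS mean, SE = 0.4976/sqrt(8) = 0.1759, factor each side | 1.36 | 1.51 |
| Power for a true 2-fold difference, one comparison | 84.2% | 66.6% |

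**3. Power for severe versus healthy under the staged design.** Here k = 3 applies only when Part A triggers Part B, so 66.6% is not the right figure for this comparison. A simulation of 1,000,000 runs with true ratio 2 used k = 3 if the observed ratio was at least 2 and k = 1 otherwise.
- Trigger on AUC alone: 82.8%
- Trigger on AUC or Cmax, with Cmax CV 56% from protocol Table 2: about 75%, 77%, 79% and 82% at assumed AUC–Cmax correlations of 0, 0.5, 0.8 and 0.95

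The documents do not give this correlation. The trigger was applied to total concentrations only.

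**4. Sensitivity to k.** Suppose the three parameters are counted as hypotheses too. With Part B, k = 3 × 3 = 9: a 98.9% interval, 66% wider, and an observed ratio of 2.0 would carry 0.97 to 4.14, which includes 1. Counting both analytes as well gives k = 18: 99.4%, 86% wider. On such readings k would exceed 1 even in Part A alone.

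**The case against.** The case for treating this as minor has real content.

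- **Part B may well not run.** Protocol 1.4 reports less than 1% of the dose in urine and no renal effect in the population PK model, though the severe group was too small to judge. Under the plan's CV, the chance of an observed AUC ratio of at least 2 is P(Z > ln(2/true ratio)/0.2488): 0.3% at a true ratio of 1.0, 2.9% at 1.25 and 12.4% at 1.5. This stands, and it limits how often the defect would appear. It does not make the text right for the stage in which it applies.
- **Power is a weak argument.** Both documents say that no prospective power calculation was made, and the intervals are illustrative. At a true ratio of 2, once AUC has triggered Part B, the k = 3 interval still excludes 1 in about 97% of runs. Also, most of the plan requires the increase in both total and unbound exposure, which would trigger less often than the simulation assumes and so lose less power. All this stands. The main defect is the wrong label, not the lost power.
- **Family-wise control is legitimate, and wider is conservative.** True as a design choice: the protocol leaves detail to the SAP, and the Bonferroni rule is stated openly in two places. One could also call the set simultaneous 90% intervals, but the SAP never does; a reader would take each tabulated interval as an ordinary 90% one. In a study that estimates an exposure increase, excess width is a loss of precision. On any reading, k must be defined and the change declared.

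**Conclusion.** The concern holds and should be fixed. The correction is absent from the protocol, enters the interval limits through the code, is contradicted by the 90% label in SAP 3.1.7 and 3.2.2.4.1, and is missing from SAP Section 5. If Part B runs and k = 3, the ANOVA intervals are 96.7% intervals, 34% wider on the log scale than the protocol promises. The widening assumes eight subjects per group; with exclusions that bring df down to between 10 and 13 it is 34% to 36%. The limits in ratio units also assume the 53% CV. If only Part A runs and k counts impaired groups, there is no discrepancy and the 84% power stands. The point estimates and the observed 2-fold rule for starting Part B are untouched in every case. Confidence is high on the contradiction itself; the exact figures depend on reading k as the number of impaired groups.

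**What to change.** **Preferred.** Set `alpha=0.10` in both the LSMEANS and ESTIMATE statements, delete SAP 3.1.6 and delete the matching Bonferroni sentence in 3.2.2.4.1. Every ANOVA interval is then the protocol's 90% interval, including those for the unbound parameters that reuse the code.

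**If the correction is kept.**
- Define k in SAP 3.1.6 as the number of impaired groups compared with healthy.
- Leave the single-group LS-mean intervals at 90%.
- Label the ratio intervals 100(1 − 0.10/k)% in 3.1.7, 3.2.2.4.1 and the tables.
- State in 1.3.4 that 84% power applies only at k = 1, and is about 67% for a single comparison at k = 3.
- List the change in Section 5.

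**Cost.** SAP wording and one option in two code statements; no new data. The preferred route gives up family-wise control over the three group comparisons, which the protocol never claimed.

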1 INFORMATION TAKEN FROM THE PROTOCOL

1.1 Study objectives

1.1.1 *Primary objective*

The primary objective of the study is to compare the pharmacokinetics (PK) of telotristat ethyl and its active metabolite telotristat (LP-778902) following a single oral dose of 250 mg telotristat ethyl in subjects with renal impaired function versus the PK in healthy subjects with normal renal function.

1.1.2 *Secondary Study Objectives*

The secondary objectives of the study are:

- to compare the safety and tolerability of a single oral dose of 250 mg telotristat ethyl in subjects with renal impaired function versus healthy subjects with normal renal function;
- to assess the effect of impaired renal function on protein binding of telotristat ethyl and its active metabolite telotristat (LP-778902);
- to evaluate the PK of the inactive metabolite LP-951757 following a single oral dose of 250 mg telotristat ethyl in subjects with renally impaired function and healthy subjects with normal renal function.

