1.2 Study design

This study is an open-label single dose staged study with Part B contingent upon the results of Part A. Part A will include two groups, a test group and a control group. The test group will include subjects with a Glomerular Filtration Rate (GFR) as low as possible i.e. < 20 mL/min, but not requiring dialysis (subjects with severely impaired renal function). If inclusion of such subjects is not possible, subjects with severely decreased renal function and a GFR between 15 and 29 ml/min (both inclusive) may be included. The test group will be compared to a control group of demographically-matched healthy subjects with normal renal function (i.e. with a GFR equal or above 90 mL/min).

The PK and protein binding analysis of telotristat ethyl, its active metabolite telotristat (LP-778902) and the inactive metabolite LP-951757 will be assessed in eight subjects with severely decreased renal function and compared to those in eight demographically-matched subjects with normal renal function (GFR \geq 90 mL/min) following single oral dose of 250 mg telotristat ethyl. If results of Part A show a substantial effect (set as 2-fold increase in total and unbound of either the maximal plasma concentration (C_{max}) or plasma exposure (AUC) of the active metabolite telotristat (LP-77902)), the PK and protein binding analysis of telotristat ethyl, its active metabolite telotristat (LP-778902) and the inactive metabolite LP-951757 will also be assessed in eight subjects with a mildly (GFR between 60 and 89 mL/min, both inclusive) and eight subjects with a moderately (GFR between 30 and 59 mL/min, both inclusive) decreased renal function (Part B) following single oral dose of 250 mg telotristat ethyl. Safety and tolerability of the single oral dose of 250 mg telotristat ethyl will also be evaluated.

Renal function will be classified based on estimated GFR as determined by the Modification of Diet in Renal Disease (MDRD) formula.

After a maximum 28-day screening period (56 days for subjects with mildly and moderately impaired renal function), eligible subjects will begin their stay at the clinical unit on Day-1 (admission day). Subjects will receive a single oral dose of telotristat etiprate (as one tablet containing 250 mg telotristat ethyl) on Day 1.

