3.1.4 Protein binding endpoints

The unbound concentrations for telotristat ethyl, its active metabolite telotristat (LP-778902) and its inactive metabolite (LP-951757) will be derived at each time point available as follows : $C_u = C_{Total} * \text{mean}(f_u)$, where $\text{mean}(f_u)$ represents the mean of the unbound fractions by timepoint.

The following PK parameters for unbound telotristat ethyl and its active metabolite telotristat (LP-778902) will be calculated using the unbound fraction F_u (defined for each subject as the mean over all time points of the mean of f_u):

- C_{maxu} : Maximum plasma concentration calculated by: $C_{maxu} = C_{max} * F_u$
- AUC_{0-infu} : Area under the concentration-time curve unbound from 0 to infinity calculated by: $AUC_{0-infu} = AUC_{0-inf} * F_u$
- $AUC_{0-tlastu}$: AUC from 0 to the last quantifiable unbound concentration calculated by: $AUC_{0-tlastu} = AUC_{0-tlast} * F_u$
- CL_u/F : Apparent total clearance from plasma calculated by: $CL_u/F = CL/F * F_u$
- V_{zu}/F : Apparent volume of distribution calculated by: $V_{zu}/F = V_z/F * F_u$.

For C_{maxu} and AUC_u , the following MR (normalized and not normalized) will also be calculated:

- $MRC_{maxu} = (C_{maxu} \text{ LP-778902}) / (C_{maxu} \text{ telotristat ethyl})$
- $MRC_{maxuNorm} = (C_{maxu} \text{ LP-778902/Molecular weight(MW)}_{LP-778902}) / (C_{maxu} \text{ telotristat ethyl/MW}_{telotristat ethyl})$
- $MRAUC_{0-infu} = (AUC_{0-infu} \text{ LP-778902}) / (AUC_{0-infu} \text{ telotristat ethyl})$
- $MRAUC_{0-infuNorm} = (AUC_{0-infu} \text{ LP-778902/MW}_{LP-778902}) / (AUC_{0-infu} \text{ telotristat ethyl/MW}_{telotristat ethyl})$
- $MRAUC_{0-tlastu} = (AUC_{0-tlastu} \text{ LP-778902}) / (AUC_{0-tlastu} \text{ telotristat ethyl})$
- $MRAUC_{0-tlastuNorm} = (AUC_{0-tlastu} \text{ LP-778902/MW}_{LP-778902}) / (AUC_{0-tlastu} \text{ telotristat ethyl/MW}_{telotristat ethyl})$
- $MRC_{maxuTotal} = (C_{maxu} \text{ LP-778902}) / (C_{maxu} \text{ LP-778902} + C_{maxu} \text{ telotristat ethyl})$
- $MRC_{maxuTotalNorm} = (C_{maxu} \text{ LP-778902/MW}_{LP-778902}) / (C_{maxu} \text{ LP-778902/MW}_{LP-778902} + C_{maxu} \text{ telotristat ethyl/MW}_{telotristat ethyl})$
- $MRAUC_{0-infuTotal} = (AUC_{0-infu} \text{ LP-778902}) / (AUC_{0-infu} \text{ LP-778902} + AUC_{0-infu} \text{ telotristat ethyl})$

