14.2.3 DERIVED UNBOUND PHARMACOKINETIC DATA

Table 14.2.3.1.1: Telotristat Ethyl Unbound Plasma Concentrations (unit) (Summary Statistics) – Pharmacokinetic Population

Table 14.2.3.1.2: LP-778902 Unbound Plasma Concentrations (unit) (Summary Statistics) – Pharmacokinetic Population

SAP Final Version 2.0: 04 June 2018				41/43
Table	14.2.3.1.3:	LP-951757 Unbound Plasma Concentrations (unit) (Summary Statistics) – Pharmacokinetic Population		
Table	14.2.3.2.1:	Telotristat Ethyl Unbound Pharmacokinetic Parameters and Unbound Fractions (Summary Statistics) – Pharmacokinetic Population		
Table	14.2.3.2.2:	LP-778902 Unbound Pharmacokinetic Parameters and Unbound Fractions (Summary Statistics) – Pharmacokinetic Population		
Table	14.2.3.2.3:	LP-951757 Unbound Pharmacokinetic Parameters and Unbound Fractions (Summary Statistics) – Pharmacokinetic Population		
Table	14.2.3.2.4:	Metabolic Ratios for Unbound Pharmacokinetic Parameters (Summary Statistics) – Pharmacokinetic Population		
Figure	14.2.3.3.1:	Scatter Plots of C_{maxu} , $AUC_{0-tlastu}$, AUC_{0-inf} and unbound fractions for Telotristat Ethyl – Pharmacokinetic Population		
Figure	14.2.3.3.2:	Scatter Plots of C_{maxu} , $AUC_{0-tlastu}$, AUC_{0-inf} and unbound fractions for LP-778902 – Pharmacokinetic Population		
Figure	14.2.3.3.3:	Scatter Plots of C_{maxu} , $AUC_{0-tlastu}$, AUC_{0-inf} and unbound fractions for LP-951757 – Pharmacokinetic Population		
Figure	14.2.3.4.1:	Box-Whisker Plots of C_{maxu} , $AUC_{0-tlastu}$, AUC_{0-inf} and unbound fractions for Telotristat Ethyl – Pharmacokinetic Population		
Figure	14.2.3.4.2:	Box-Whisker Plots of C_{maxu} , $AUC_{0-tlastu}$, AUC_{0-inf} and unbound fractions for LP-778902 – Pharmacokinetic Population		
Figure	14.2.3.4.3:	Box-Whisker Plots of C_{maxu} , $AUC_{0-tlastu}$, AUC_{0-inf} and unbound fractions for LP-951757 – Pharmacokinetic Population		
Table	14.2.3.5.1.1:	Comparison of C_{maxu} , $AUC_{0-tlastu}$, AUC_{0-inf} and unbound fractions for Telotristat Ethyl between each Renal Impairment Group and Healthy Control Group (ANOVA) – Pharmacokinetic Population		
Table	14.2.3.5.1.2:	Comparison of C_{maxu} , $AUC_{0-tlastu}$, AUC_{0-inf} and unbound fractions for Telotristat Ethyl between each Renal Impairment Group and Healthy Control Group (ANOVA) – Sensitivity analysis – Pharmacokinetic Population		

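### The design text says LP-951757 will be compared between severe and matched normal subjects, but the SAP plans only group summaries and plots for it, and it lists unbound LP-951757 parameters without formulas

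*SAP*

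**What the plan says.** **Design text.** In the protocol synopsis and SAP 1.2, the sentence on PK and protein binding covers all three analytes: "and the inactive metabolite LP-951757 will be assessed in eight subjects with severely decreased renal function and compared to those in eight demographically-matched subjects". The matched subjects are the healthy controls.

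**Objectives and endpoints.** The secondary objective for this analyte is "to evaluate the PK of the inactive metabolite LP-951757 following a single oral dose of 250 mg telotristat ethyl" in both kinds of subject. The protein-binding objective names only telotristat ethyl and telotristat. Protocol 3.2.2 makes the bound and unbound percentages of all three analytes a secondary endpoint.

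**Analysis.** SAP 3.2.2.4.1 specifies the ANOVA on log Cmax, AUC0-tlast and AUC0-inf "for both telotristat ethyl and its active metabolite with renal function group as a fixed term". SAP 3.2.2.4.3 uses the same wording for the unbound parameters and for fu, which is analysed without log transformation. Protocol 11.4.4 also restricts its ANOVA to these two analytes.

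**Unbound derivation.** SAP 3.1.4 derives unbound concentrations for all three analytes, then narrows: "The following PK parameters for unbound telotristat ethyl and its active metabolite telotristat (LP-778902) will be calculated using the unbound fraction". SAP 3.2.2.4.3 nevertheless plans descriptive statistics on unbound parameters for LP-951757 as well. Appendix 2 provides the outputs: Table 14.2.3.2.3, Figures 14.2.3.3.3 and 14.2.3.4.3, and Listing 16.2.5.10.3.

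**The concern.** There are two mismatches.

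1. The design text names LP-951757 among the analytes to be compared, but the section that produces comparisons leaves it out. SAP 3.2.2.1 notes that no quantitative human exposure data on LP-951757 after oral dosing are available yet. This study could give a first estimate of how severe renal impairment changes that exposure. Without a pre-specified ratio and interval, the report would show two sets of group statistics and leave readers to judge the size of the difference and how imprecise it is.

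2. The output list requires unbound LP-951757 parameters for which the SAP gives no calculation rule. A programmer would have to assume one or drop the outputs.

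**Working it through.** **Step 1. Trace LP-951757 through the SAP.**

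| Item | LP-951757 covered? | Where |
|---|---|---|
| Total PK parameters, summarised by group (geometric mean and geometric CV included) | Yes | SAP 3.1.3, 3.2.2.2; Table 14.2.1.3.3 |
| Scatter and box plots against control; plots against eGFR | Yes | SAP 3.2.2.4.1; Figures 14.2.1.4.3, 14.2.1.5.3, 14.2.1.6.3 |
| Unbound concentrations (formula) | Yes | SAP 3.1.4; Appendix 1 item 10 |
| fu by group | Yes | SAP 3.2.2.4.3; Table 14.2.3.2.3 |
| Unbound parameters (formulas) | **No**, though outputs are listed | SAP 3.1.4 against 3.2.2.4.3 and Appendix 2 |
| ANOVA ratio and CI, total exposure | **No** | SAP 3.2.2.4.1; only Tables 14.2.1.7.1.x and 14.2.1.7.2.x |
| ANOVA on unbound parameters and fu | **No** | SAP 3.2.2.4.3; only Tables 14.2.3.5.1.x and 14.2.3.5.2.x |
| tmax difference and CI | **No** table | Only Tables 14.2.1.8.1 and 14.2.1.8.2 |

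For tmax, the text of SAP 3.2.2.4.1 names no analyte. The restriction shows only in the table index.

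**Step 2. Reproduce the plan's own design figure.** Protocol 11.2 gives 84% power for a 2-fold difference in AUCinf with 8 per group and CV 53%.

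- Log-scale SD = √ln(1 + 0.53²) = 0.498.
- SE of the difference = 0.498 × √(2/8) = 0.249.
- Noncentrality = ln 2 / 0.249 = 0.693 / 0.249 = 2.79, with 14 df.
- Two-sided alpha 0.10, noncentral t: power = 84.2%.

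The stated 84% reproduces, which supports using the same model in the next step.

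**Step 3. Precision if the same ANOVA were run on LP-951757.** The 90% CI is the ratio multiplied and divided by exp(t × SD × √(2/8)), with t(0.95, 14 df) = 1.761. The documents give no CV for LP-951757, so these CVs are assumptions:

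| Assumed CV | Log SD | SE | Factor | CI around an observed ratio of 100% |
|---|---|---|---|---|
| 30% | 0.294 | 0.147 | 1.30 | 77.2% to 129.5% |
| 53% (telotristat's value) | 0.498 | 0.249 | 1.55 | 64.5% to 155.0% |
| 80% | 0.703 | 0.352 | 1.86 | 53.8% to 185.8% |

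At CV 53%, an observed ratio of 2 would carry an interval of 2/1.55 = 1.29 to 2 × 1.55 = 3.10. That is wide, but informative for an analyte with no earlier exposure data.

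**Step 4. Effect of the multiplicity rule.** SAP 3.1.6 divides the 10% level by the number of hypotheses. With three hypotheses, the factor at CV 53% would rise from 1.55 to 1.80. The SAP therefore has to say whether an added LP-951757 analysis counts.

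**The case against.** The strongest defence is that the SAP follows the protocol's analysis section. Protocol 11.4.4 restricts the ANOVA to two analytes, protocol 8 does the same for the unbound parameters, and the body text of protocol 3.1 describes the PK and protein-binding evaluation for those two. The LP-951757 objective is to evaluate, not to compare. A design paragraph that uses the word compared does not by itself promise a ratio with an interval. All of this stands, and it limits the severity. It does not reconcile the synopsis and SAP 1.2 with the analysis sections.

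A reader might infer that the LP-951757 comparison is never estimated. The documents do not support that. If at least 2/3 of values are determined, each group gets a geometric mean, geometric CV and n. The ANOVA has two groups and no covariates, so its ratio and interval for Cmax and AUC can be rebuilt from those statistics, apart from rounding. Plots against control and eGFR are also planned. What is missing is a pre-specified, printed effect size and interval.

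A reader might also infer that LP-951757 has no unbound derivation. That is too broad: unbound concentrations and fu are covered, and only the unbound parameter formulas leave it out.

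Expected low concentrations could explain descriptive reporting, since SAP 3.2.2.1 warns that some LP-951757 values may fall below the quantification limit. But the same section gives a similar warning for telotristat ethyl, which is still modelled, protected by the rule that no analysis is done if more than 1/3 of values are undetermined. The same rule would serve LP-951757.

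**Conclusion.** The point holds as a mismatch between the design text and the analysis. LP-951757 is named for comparison with matched normal subjects, yet only group summaries and plots are planned. The unbound-parameter inconsistency within the SAP is separate and would remain even if descriptive reporting was intended.

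The severity is low. The primary objective and primary endpoint concern telotristat ethyl and telotristat, and the Part B decision rests on telotristat alone (protocol 11.4.5, SAP 3.2.17). The secondary objective, which asks for evaluation, can be met descriptively.

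The gain from the fix is a stated ratio with a 90% CI of about ×/÷ 1.30 to 1.86. This assumes eight evaluable subjects per group and a CV between 30% and 80%. Fewer determined values would widen it.

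**What to change.** 1. In SAP 3.2.2.4.1 and 3.2.2.4.3, run the existing two-group ANOVA for LP-951757 Cmax, AUC0-tlast, AUC0-inf and fu (for fu, a difference in means, as it is not log-transformed). Keep the existing 1/3 rule.
2. Add LP-951757 to the tmax tables and add the matching ANOVA tables to Appendix 2.
3. Label these analyses secondary or exploratory, report unadjusted 90% CIs, and state that they lie outside the Bonferroni count in SAP 3.1.6.
4. Extend the unbound parameter formulas in SAP 3.1.4 to LP-951757 so that they match SAP 3.2.2.4.3 and the Appendix 2 outputs. Check the clearance and volume formulas before copying them: if AUCu = AUC × Fu, then dose/AUCu equals CL/F divided by Fu, whereas SAP 3.1.4 multiplies by Fu.

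If the sponsor prefers a descriptive comparison, the minimum is to say so in the SAP; item 4 is still needed.

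The cost is SAP wording, a few table shells and reuse of existing code. The samples and data are already planned.
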